6.3.2 Dose adjustments for QTcF prolongation

If QTcF >500 msec or QTcF prolongation >60 msec from baseline is observed at any point during study treatment, and confirmed, the below guidance must be followed:

1. Assess the quality of the ECG recording and the QT value and repeat if needed
2. Interrupt study treatment until confirmed resolution of QTcF and as per dose reduction guidelines for non-hematological AEs.
3. Determine the serum electrolyte levels (in particular hypokalemia, hypomagnesemia). If abnormal, correct abnormalities before resuming study drug treatment.
4. Review concomitant medication associated with QT prolongation, including drugs with a “Known”, “Possible”, or “Conditional risk of Torsades de Pointes” (refer to www.crediblemeds.org/), and drugs with the potential to increase the risk of study drug exposure related QT prolongation.
5. Check study drug dosing schedule and treatment compliance.

After confirming ECG reading at site, if QTcF > 500 msec

- Interrupt study treatment
- Repeat ECG and confirm ECG diagnosis by a cardiologist or central ECG lab
- If QTcF confirmed > 500 msec:
 - Correct electrolytes, eliminate culprit concomitant treatments, and identify and address clinical conditions that could potentially prolong the QT as per the ECG and QTc Clinical Safety Standards Guidelines Section 3.3.1.
 - Consult with a cardiologist (or qualified specialist)
 - Increase cardiac monitoring as indicated, until the QTcF returns to ≤ 480 msec.
- After resolution to ≤ 480 msec, consider re-introducing treatment at reduced dose, and increase ECG monitoring for the next treatment(s), (e.g. pre-dose and 2 hours post dose after one week and two weeks of treatment re-introduction):

- If QTcF remains ≤ 500 msec after dose reduction, continue planned ECG monitoring during subsequent treatment
- If QTcF > 500 msec recurs after dose reduction, discontinue patient from trial.

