6.3 Dose modifications

6.3.1 Dose modification and dose delay

For patients who do not tolerate the protocol-specified dosing schedule, dose interruptions and/or reductions are either recommended or mandated in order to allow the patient to continue the study treatment.

These dose modifications are summarized in [Table 6-2](#). The dose reduction indicated as “recommendations” are provided to assist investigators in the event the patient experiences toxicity. However, deviations from “mandatory” dose interruptions and/or reductions are not allowed and mandatory interruptions or reductions must be strictly followed. Re-escalation to asciminib 40 mg BID is permitted if a change in the patient’s individual benefit/risk assessment at the lower dose level is seen. Re-escalation will be allowed only once for any given patient on the asciminib arm per protocol. Permanent treatment discontinuation is mandatory for specific events indicated as such in [Table 6-2](#). Any dose changes must be recorded on the Dosage Administration Record eCRF.

A patient must discontinue treatment with either asciminib or bosutinib if, after treatment is resumed at a lower dose level, the toxicity recurs with the same or worse severity, except for recurrence of cytopenias ([Table 6-2](#)). If a patient requires a dose interruption of > 28 days for each non-hematologic toxicity, then the patient must be discontinued from the study treatment. If a hematologic toxicity (cytopenia Grade 3 or 4) lasts for more than 42 days without recovery to at least a Grade 2, despite TKI interruption and adequate management (including hematopoietic growth factors), then the patient must be discontinued from the study treatment.

Table 6-2 Criteria for dose reduction/interruption and re-initiation of asciminib and bosutinib treatment for adverse drug reactions

[figure not shown]
Dose modifications for both asciminib and bosutinib		
Please note that if a patient requires a dose interruption of > 28 days for each toxicity, then the patient must be discontinued from the study treatment		
Worst toxicity CTCAE Grade 4.03	Asciminib	Bosutinib
Investigations (Hematologic) If a hematologic toxicity (cytopenia Grade 3 or 4) lasts for more than 42 days without recovery to at least a Grade 2, despite TKI interruption and adequate management (including hematopoietic growth factors), then the patient must be discontinued from the study treatment.		
Neutropenia (ANC)		

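### Section 6.3.2 interrupts treatment on two QTcF scales but sets restart and after-restart limits on one, so a value that still meets the interruption trigger can fall within the limits for being on drug

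*Combined protocol and SAP*

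**What the plan says.** Section 6.3.2 (Dose adjustments for QTcF prolongation) applies to both arms. Its opening condition uses two scales, an absolute value and a change: "If QTcF >500 msec or QTcF prolongation >60 msec from baseline is observed at any point during study treatment". If either is confirmed, five steps are mandatory. The second is "Interrupt study treatment until confirmed resolution of QTcF and as per dose reduction guidelines for non-hematological AEs". It gives no msec value and no scale for resolution.

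A separate block then begins "After confirming ECG reading at site, if QTcF > 500 msec". All the later limits are in this block:

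- Restart: "After resolution to ≤ 480 msec, consider re-introducing treatment at reduced dose".
- After restart, going on: "If QTcF remains ≤ 500 msec after dose reduction, continue planned ECG monitoring during subsequent treatment".
- After restart, stopping: a return above 500 msec takes the patient off the trial.

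The change from baseline does not appear again after the opening condition. Table 6-2, to which the second step points, has no QT row; its general non-hematologic rows act by CTCAE grade. Section 6.3.1 adds a general rule that treatment must be discontinued if "after treatment is resumed at a lower dose level, the toxicity recurs with the same or worse severity", with an exception only for cytopenias.

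**The concern.** A rule that stops treatment on two scales and releases it on one is consistent only if meeting the release limit guarantees that neither stopping condition still holds. Here it does not. The change-from-baseline trigger applies throughout treatment and nothing switches it off after re-introduction, yet the restart and after-restart lines look only at the absolute value. A patient can therefore satisfy the stated limit for going back on drug, or be within the stated range for staying on it, while the mandatory interruption condition is still met.

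There is also a gap. A patient who never exceeds 500 msec but rises more than 60 msec above baseline must be interrupted, but does not enter the block that holds the numbers.

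What is at stake is patient safety, and whether sites in an open-label trial handle the same ECG in the same way.

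**Working it through.** The plan states no figure here to reproduce, so this is a check of whether the thresholds are compatible.

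Inputs:

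- Interruption trigger (6.3.2): QTcF > 500, or QTcF − b > 60, where b is the patient's baseline.
- Restart limit (6.3.2, block for values above 500): QTcF ≤ 480.
- After-restart range for going on (same block): QTcF ≤ 500.
- Eligible baselines (5.3, exclusion criterion 5): b below 450 msec for men and below 460 for women.

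**At restart.** The limit and the trigger hold together when b + 60 < QTcF ≤ 480. The width is 480 − (b + 60) = 420 − b, so an overlap exists for every b < 420.

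**After restart.** They hold together when b + 60 < QTcF ≤ 500. The width is 500 − (b + 60) = 440 − b, so an overlap exists for every b < 440.

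In whole msec:

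| Baseline b | Change trigger met from | Overlap with restart limit | Overlap with after-restart range |
|---|---|---|---|
| 380 | 441 | 441–480 | 441–500 |
| 400 | 461 | 461–480 | 461–500 |
| 420 | 481 | none | 481–500 |
| 430 | 491 | none | 491–500 |
| 440 | 501 | none | none |

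From a baseline of 440 upwards there is no conflict, because a rise of more than 60 msec already means a value above 500. Both cut-points, 420 and 440, lie inside the eligible range.

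**Patient in the block for values above 500.** Take b = 400. Exceeding 500 means a rise of more than 100 msec, so both triggers were met. QTcF then falls to 470. That is within the limit at which restart may be considered, and it is still 470 − 400 = 70 msec above baseline. If QTcF is later 490 on the reduced dose, it is within the range for going on and is 90 msec above baseline, so the opening condition again calls for interruption.

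**Patient who triggers on the rise only.** Take b = 400 and a peak of 490. The rise is 90 msec and interruption is mandatory. The patient never exceeded 500, so the 480 and 500 limits do not formally apply. The second step sends the site to rows that act by grade, but 6.3.2 assigns no grade to a QTcF value. For asciminib those rows differ in consequence: Grade 2 resumes at the same dose, Grade 3 at a reduced dose, and Grade 4 ends treatment.

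**The case against.** The strongest reply is that the sentences do not command opposite things. Restart is only to be considered, and the line for values up to 500 literally instructs ECG monitoring. The opening condition is mandatory throughout treatment, so a site that interrupts whenever it is met disobeys nothing. A reader might infer that one ECG requires both interrupting and continuing; the text does not go that far. What stands is narrower. The line on values up to 500 presupposes ongoing treatment, it is paired with a line that removes the patient above 500, and no sentence says which prevails.

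A second reply is that the rise-only patient is covered by Table 6-2, with resolution by grade and a 28-day limit on interruption. CTCAE grading may supply the mapping to msec, but it is not in these documents. Section 6.3.2 also cites a QTc safety guideline that is not available here.

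Four other inferences are tempting and are not supported:

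- *A three-way conflict with 6.3.1.* With a baseline of 400, a patient who first exceeded 500 and later shows 490 is lower on both scales, so recurrence at the same or worse severity is not evident. A patient who triggered only on the rise never reached the line on 500. How 6.3.1 treats a recurrent rise is simply unstated.
- *A clash between considering restart and the mandatory Grade 3 reduction.* One concerns whether to restart, the other the dose if treatment is restarted. Both point to a reduced dose.
- *That this is the trial's only QT safeguard.* QTcF limits also govern entry (5.3), Day 1 dosing (7.2.2.6.1) and the switch to asciminib (7.1.2.2), and 6.4.3 covers QT-prolonging drugs.
- *That the primary endpoint is put at risk.* Section 10.4.3 counts discontinuation of randomized treatment before Week 24 as non-response; an interruption is not that. Recruitment was completed on 22 October 2019 and the latest amendment is dated 5 August 2020, more than 40 weeks later, so a further amendment would come after the Week 24 window.

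**Conclusion.** The point holds in two parts. For a patient re-introduced through the block for values above 500 msec, the restart limit overlaps the interruption trigger at any baseline below 420, and the after-restart range overlaps it at any baseline below 440. For a patient who triggers only on the rise, 6.3.2 gives no QTcF value for resolution and no after-restart rule.

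The number affected is probably small. Section 1.2.1.2 reports, for asciminib monotherapy, no rise above 60 msec and two new values above 500, neither at 40 mg BID. It gives no figures for bosutinib, so frequency in that arm is not bounded by this evidence.

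The conclusion assumes that baseline in 6.3.2 means the pre-treatment QTcF, and that the opening condition remains in force after re-introduction, since nothing limits it. If resolution in the second step was meant to cover the change scale too, the restart overlap eases; the after-restart overlap does not.

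**What to change.** The sponsor should reconcile the sentences of 6.3.2 with each other, with the non-hematologic rows of Table 6-2 and with the recurrence rule in 6.3.1. The revised text should state:

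- how the change-from-baseline trigger applies when restart is considered and after re-introduction;
- what counts as resolution, and what happens after restart, for a patient who triggered only on the rise;
- which sentence prevails when the absolute limit is satisfied but the change-from-baseline trigger is still met;
- whether the 6.3.1 recurrence rule applies to QTcF, and how QTcF values map to the grades in Table 6-2.

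Which limits to use is for the sponsor's clinical team. The cost is a few sentences at the next amendment and a note to sites. No new ECGs are needed.

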6.3.3 Follow-up for toxicities

Patients whose treatment is permanently discontinued due to a study drug related adverse event or clinically significant laboratory value, must be followed up at least once a week for 4 weeks, until resolution or stabilization of the event, whichever comes first. Appropriate clinical experts such as ophthalmologist, endocrinologist, dermatologist, psychiatrists etc. should be consulted as deemed necessary. All patients must be followed up for adverse events and serious adverse events for 30 days following the last dose of study treatment.

6.3.3.1 Follow up on potential drug-induced liver injury (DILI) cases

Patients with transaminase increase combined with TBIL increase may be indicative of potential DILI, and should be considered as clinically important events.

The threshold for potential DILI may depend on the patient's baseline AST/ALT and TBIL value; patients meeting any of the following criteria will require further follow-up as outlined below:

- For patients with normal ALT and AST and TBIL value at baseline: AST or ALT > 3.0 x ULN combined with TBIL > 2.0 x ULN
- For patients with elevated AST or ALT or TBIL value at baseline: [AST or ALT > 2 x baseline AND > 3.0 x ULN] OR [AST or ALT > 8.0 x ULN], combined with [TBIL > 2 x baseline AND > 2.0 x ULN]

Medical review needs to ensure that liver test elevations are not caused by cholestasis, defined as ALP elevation > 2.0 x ULN with R value < 2 in patients without bone metastasis, or elevation of ALP liver fraction in patients with bone metastasis.

Note: (The R value is calculated by dividing the ALT by the ALP, using multiples of the ULN for both values. It denotes whether the relative pattern of ALT and/or ALP elevation is due to cholestatic ($R \leq 2$), hepatocellular ($R \geq 5$), or mixed ($R > 2$ and < 5) liver injury).

In the absence of cholestasis, these patients should be immediately discontinued from study drug treatment, and repeat LFT testing as soon as possible, preferably within 48 hours from the awareness of the abnormal results. The evaluation should include laboratory tests, detailed history, physical assessment and the possibility of liver metastasis or new liver lesions, obstructions/compressions, etc.

1. Laboratory tests should include ALT, AST, albumin, creatinine kinase, total bilirubin, direct and indirect bilirubin, GGT, prothrombin time (PT)/INR and alkaline phosphatase.
2. A detailed history, including relevant information, such as review of ethanol, concomitant medications, herbal remedies, supplement consumption, history of any pre-existing liver conditions or risk factors, should be collected.
3. Further testing for acute hepatitis A, B, C or E infection and liver imaging (e.g. biliary tract) may be warranted.

4. Obtain PK sample, as close as possible to last dose of study drug, if PK analysis is performed in the study.
5. Additional testing for other hepatotropic viral infection (CMV, EBV or HSV), autoimmune hepatitis or liver biopsy may be considered as clinically indicated or after consultation with specialist/hepatologist.

All cases confirmed on repeat testing meeting the laboratory criteria defined above, with no other alternative cause for LFT abnormalities identified should be considered as “medically significant”, thus, met the definition of SAE ([Section 8.2.1](#)) and reported as SAE using the term “potential drug-induced liver injury”. All events should be followed up with the outcome clearly documented.

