 - Hematologic intolerance: Patients with grade 3 or 4 toxicity (absolute neutrophil count [ANC] or platelets) while on therapy that is recurrent after dose reduction to the lowest doses recommended by manufacturer
6. Eastern Cooperative Oncology Group (ECOG) performance status (PS) of 0, 1, or 2
7. Adequate end organ function as defined by (as per central laboratory tests):
 - Total bilirubin $\leq 1.5 \times$ ULN except for patients with Gilbert's syndrome who may only be included if total bilirubin $\leq 3.0 \times$ ULN or direct bilirubin $\leq 1.5 \times$ ULN

- Aspartate transaminase (AST) $\leq 3.0 \times \text{ULN}$
 - Alanine transaminase (ALT) $\leq 3.0 \times \text{ULN}$
 - Serum lipase $\leq 1.5 \times \text{ULN}$. For serum lipase $> \text{ULN} - \leq 1.5 \times \text{ULN}$, value must be considered not clinically significant and not associated with risk factors for acute pancreatitis
 - Alkaline phosphatase $\leq 2.5 \times \text{ULN}$
 - Creatinine clearance $\geq 50 \text{ mL/min}$ as calculated using Cockcroft-Gault formula
8. Patients must avoid consumption of grapefruit, Seville oranges or products containing the juice of each during the entire study and preferably 7 days before the first dose of study medications, due to potential CYP3A4 interaction with the study medications. Orange juice is allowed.
9. Written informed consent obtained prior to any screening procedures.
- 10a. Patients must have the following electrolyte values (as per central laboratory tests) within normal limits or corrected to be within normal limits with supplements prior to first dose of study medication:
- Potassium (potassium increase of up to 6.0 mmol/L is acceptable at study entry if associated with creatinine clearance within normal limits)
 - Total calcium (corrected for serum albumin); (calcium increase of up to 12.5 mg/dl or 3.1 mmol/L is acceptable at study entry if associated with creatinine clearance within normal limits)
 - Magnesium, with the exception of magnesium increase $> \text{ULN} - 3.0 \text{ mg/dL}$; $> \text{ULN} - 1.23 \text{ mmol/L}$ associated with creatinine clearance (calculated using Cockcroft-Gault formula) within normal limits.
11. Evidence of typical BCR-ABL1 transcript [e14a2 and/or e13a2] at the time of screening which are amenable to standardized RQ-PCR quantification.

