> 20.0 x ULN	Mandatory: Hold dose. Repeat LFTs ^b as soon as possible, preferably within 48-72 hours from awareness of the abnormal results; monitor LFTs ^b weekly, or more frequently if clinically indicated, until resolved to ≤ 3 x ULN (or ≤ 5 x ULN for patients with baseline value > 3.0 -5.0 x ULN), then resume treatment at reduce dose ↓ 1 dose level. Only 1 dose reduction is allowed; if reoccurs at > 5 x ULN, discontinue patient from study drug treatment.	Mandatory: Hold dose. Repeat LFTs ^b as soon as possible, preferably within 48-72 hours from awareness of the abnormal results; monitor LFTs ^b weekly, or more frequently if clinically indicated, until resolved to ≤ 2.5 x ULN (then Recommendation: If resolved in ≤ 28 days, reduce dose ↓ 1 dose level maintain dose level Recommendation: If resolved in > 28 days, Discontinue patient from study drug treatment

Dose modifications for both asciminib and bosutinib		
Please note that if a patient requires a dose interruption of > 28 days for each toxicity, then the patient must be discontinued from the study treatment		
Worst toxicity CTCAE Grade 4.03	Asciminib	Bosutinib
Combined ^c elevations of AST or ALT and total bilirubin		
For patients with normal baseline ALT and AST and total bilirubin value: AST or ALT >3.0 x ULN combined with total bilirubin >2.0 x ULN without evidence of cholestasis ^d For patients with elevated baseline AST or ALT or total bilirubin value [AST or ALT >2 x baseline AND > 3.0 x ULN]	Mandatory: Permanently discontinue patient from study drug treatment. Repeat as soon as possible, preferably within 48 hours from awareness of the abnormal results, then with weekly monitoring of LFTs ^b), or more frequently if clinically indicated, until AST, ALT, or bilirubin have resolved to baseline or stabilization over 4 weeks. Refer to Section 6.3.3.1 for additional follow-up evaluations as applicable.	Mandatory: Permanently discontinue patient from study drug treatment. Repeat as soon as possible, preferably within 48 hours from awareness of the abnormal results, then with weekly monitoring of LFTs ^b), or more frequently if clinically indicated, until AST, ALT, or bilirubin have resolved to baseline or stabilization over 4 weeks. Refer to Section 6.3.3.1 for additional follow-up evaluations as applicable.
Investigation (metabolic)		
Asymptomatic amylase and/or lipase elevation		

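### An eligible, unchanged entry ALP above 2.0 x ULN can count as cholestasis and lift the mandatory permanent stop for combined ALT/AST and bilirubin elevation in patients with normal baseline ALT, AST and bilirubin

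*Combined protocol and SAP*

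**What the plan says.** - **Entry.** Section 5.2, criterion 7, accepts ALP up to 2.5 x ULN.
- **Definition.** In Section 6.3.3.1 cholestasis is "defined as ALP elevation > 2.0 x ULN with R value < 2 in patients without bone metastasis"; note d of Table 6-2 has the same cut-offs. "The R value is calculated by dividing the ALT by the ALP, using multiples of the ULN for both values", so AST plays no part in R. The alternative branch is "or elevation of ALP liver fraction in patients with bone metastasis".
- **Stop.** The normal-baseline row of Table 6-2 orders permanent discontinuation for "AST or ALT >3.0 x ULN combined with total bilirubin >2.0 x ULN without evidence of cholestasis". Section 6.3.3.1 says, for both baseline groups, "In the absence of cholestasis, these patients should be immediately discontinued from study drug treatment".
- **Baseline adjustment.** Where ALT, AST or bilirubin was raised at entry, Section 6.3.3.1 sets the AST/ALT and bilirubin thresholds relative to baseline; the bilirubin term is "TBIL > 2 x baseline AND > 2.0 x ULN". ALP has no such term.
- **Fallback.** Note c of Table 6-2 sends cases that miss the combined thresholds to the isolated bilirubin and AST/ALT rows. It asks for the more cautious action when two rows differ, and allows restart only once all values have recovered to their restart levels.

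**The concern.** ALP decides whether the combined-elevation stop applies, yet it is the one liver parameter in the rule with no baseline comparison. The ALP half of the exemption can therefore be met before the first dose by a patient the protocol accepts. The same unchanged ALP also sits in the denominator of R, which makes R < 2 easier to meet.

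Section 1.2.1.1 lists the liver among the potential target tissues in the animal studies, so this stop is a real safeguard. At stake is whether a finding that cannot be due to study drug should turn a mandatory permanent stop into a hold with possible restart.

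**Working it through.** The plan gives no figure to reproduce; this is threshold logic. All values are multiples of ULN, and ALT, AST and bilirubin are normal at baseline.

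**Rules as written**
- Trigger: (ALT > 3.0 or AST > 3.0) and bilirubin > 2.0.
- Cholestasis: ALP > 2.0 and R = ALT / ALP < 2, which is the same as ALT < 2 x ALP.
- Permanent stop: trigger met and cholestasis absent.

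**ALT-led cases, ALP unchanged from entry**

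| ALP | ALP > 2.0? | 2 x ALP | ALT range in which the stop is lifted | Width |
|---|---|---|---|---|
| 1.9 | no | – | none | 0 |
| 2.1 | yes | 4.2 | above 3.0, below 4.2 | 1.2 |
| 2.3 | yes | 4.6 | above 3.0, below 4.6 | 1.6 |
| 2.5 | yes | 5.0 | above 3.0, below 5.0 | 2.0 |

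**Worked cases**
- A: ALT 4.0, bilirubin 2.5, ALP 2.3 at entry and now. R = 4.0 / 2.3 = 1.74: cholestatic, stop lifted.
- B (AST-led): AST 6.0, ALT 2.5, bilirubin 2.5, ALP 2.3. R = 2.5 / 2.3 = 1.09: cholestatic, stop lifted. Because R ignores AST, the label holds at any AST while ALT < 2 x ALP.
- C (contrast): ALT 4.5, bilirubin 2.5, ALP 1.9. R = 4.5 / 1.9 = 2.37 and ALP is not above 2.0: stop applies.
- D (boundary): ALT 5.0, bilirubin 3.5, ALP 2.5. R = 2.0, not below 2: stop applies.

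**What happens instead, using the isolated rows of Table 6-2 and note c**
- Case A: the ALT row (> 3.0 to 5.0) recommends keeping the dose; the bilirubin row (> 1.5 to 3.0) recommends a hold. The more cautious action is the hold. Asciminib may resume at the same dose if values resolve within 14 days, or one level lower if later. The bosutinib column reads the same in these two rows.
- Case B: AST > 5.0 to 10.0 is a mandatory hold. Asciminib again resumes at the same dose if resolved within 14 days, one level lower if later.
- Bilirubin > 3.0 to 10.0: mandatory hold, one level lower if resolved within 14 days, otherwise discontinue. Above 10.0: permanent discontinuation whatever the ALP.

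**Raised-baseline patients.** The Table 6-2 row begins "For patients with elevated baseline AST or ALT or total bilirubin value [AST or ALT >2 x baseline AND > 3.0 x ULN" and, as it could be read, carries no cholestasis condition, so its mandatory stop remains. Section 6.3.3.1 does apply the condition to this group. That is an inconsistency between the two places, and no size is claimed for it.

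**The case against.** The best case against has four parts.

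- **The fallback is safe.** A cholestatic case naturally fails the combined criterion, so note c leads to the isolated rows, applied cautiously. This stands, and it limits the point: every affected case has bilirubin above 2.0 x ULN and so gets at least a recommended hold. Section 6.3.1 also requires discontinuation after an interruption of more than 28 days, or if toxicity recurs at the same or worse severity after dose reduction. Section 7.1.6 tells the investigator to stop treatment judged harmful.
- **Medical review and isoforms would catch it.** Review asks whether cholestasis is the cause, and patients meeting the ALT/AST and bilirubin thresholds need further follow-up in any event. But review is handed the same definition. Note b requests ALP isoforms above 2.0 x ULN, yet the liver fraction enters the definition only with bone metastasis. A careful reviewer may reach the right answer; the written rule does not lead there.
- **Elevation implies a rise from baseline.** The text gives a fixed cut, and the same section writes a baseline multiple where it wants one.
- **Almost nobody qualifies.** Probably right. Exclusion 9 removes patients with a history of liver disease. This bears on severity, not on whether the rule is correct.

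A reader might infer that treatment simply continues, or that a very high AST brings no response. The documents do not support that: AST or ALT above 5.0 x ULN, or bilirubin above 3.0 x ULN, is a mandatory hold in the isolated rows. Nor do they support extending the loss of the Table 6-2 stop to raised-baseline patients, whose row as read has no cholestasis condition.

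**Conclusion.** The point holds for patients with normal baseline ALT, AST and bilirubin and an entry ALP above 2.0 and up to 2.5 x ULN. For them an unchanged ALP can replace a mandatory permanent stop with a hold and possible restart. In ALT-led cases the affected ALT range is 1.2 to 2.0 x ULN wide at ALP 2.1 to 2.5; AST-led cases are limited only by ALT < 2 x ALP. What is lost is permanence, not action.

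This assumes that the definition is applied as written and that note c governs the fallback, which is the natural reading but is not stated for cholestatic cases. The documents do not give the number of patients with entry ALP in this band; it is likely very small. Severity is minor.

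A reader might also infer that such cases escape serious adverse event reporting as potential drug-induced liver injury. Section 6.3.3.1 asks for that report when no alternative cause is identified, but does not say whether the cholestasis label counts as one, so this is only a possibility. The gap does not alter an endpoint definition or the type I error.

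**What to change.** Leave eligibility alone, since recruitment is complete (Amendment 03-US.01). In Section 6.3.3.1 and Table 6-2 note d, add: for patients with ALP above ULN at baseline, cholestasis also requires ALP > 2 x baseline. Align the raised-baseline row of Table 6-2 with Section 6.3.3.1 at the same time.

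The multiple is the one already used for AST/ALT and bilirubin. At baseline ALP 2.1, 2.3 or 2.5 the label then needs ALP above 4.2, 4.6 or 5.0 x ULN, so cases A and B are stopped. Starting the clause at ULN avoids a cliff: a baseline of 1.0 needs ALP above 2.0, matching the existing cut, and a baseline of 1.9 drifting to 2.1 no longer qualifies because it needs more than 3.8. The medical team may choose another multiple, provided an ALP at its baseline value cannot qualify.

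Baseline ALP is already in the screening chemistry (Table 7-5), so no new test is needed; the change does need an amendment under Section 12.1. The clinical cost is an occasional patient with true cholestasis and a modest ALP rise who is permanently stopped. For example, baseline ALP 2.3 rises to 4.0 with ALT 4.0 and bilirubin 2.5: R = 4.0 / 4.0 = 1.0, but 4.0 is below 4.6. Discontinuing randomized treatment in this way counts as non-response if it comes before week 24 (Section 10.4.3) and as a treatment-failure event (Section 10.5.2).
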